Cover page

Official Title of study: Behavioral Economic Analysis of Demand for Marijuana

ClinicalTrials.gov Identifier: NCT03518567

Document Type: Protocol and Statistical Analysis Plan dated 10/8/2020

Subtitle: N/A

(The informed consent form document(s) uploaded in Portable Document Format Archival (PDF/A) format. It is strongly encouraged that the PDF/A file also be consistent with the PDF Universal Accessibility (PDF/UA) format, to optimize accessibility).

RESEARCH PROTOCOL

Principal Investigator: [name].

Brown University School of Public Health Center for Alcohol and Addiction Studies

[name]

Primary Mentor/Co-Investigator: [name]., Brown University

Project Title: Behavioral Economic Analysis of Demand for Marijuana

NIDA Grant #: K01DA039311

Authority: This study has been approved by the Brown University Institutional

Review Board

A. RATIONALE AND OVERVIEW

Since 1996, 20 states (including Rhode Island) and Washington DC have legalized use of marijuana for medical purposes, and Washington and Colorado legalized recreational use of marijuana in 2012 [1]. If these trends in marijuana legislation continue, the production, advertisement, and sale of marijuana are likely to commence across the United States. The relative ease of accessibility to inexpensive marijuana is a considerable risk factor for heavy use, as is the case with alcohol [2], and marijuana legalization may amplify initiation and progression of use [3]. Due to the shift in normative perceptions surrounding marijuana use [4], an approach to analyze the value of this drug is essential. It is not only imperative, but time-sensitive, that we investigate the factors that may influence the behavioral economic demand for marijuana in this novel drug market. The goal of the present study is to develop and validate a refined measure for assessment of demand for marijuana to be used in future investigations.

B.1. SPECIFIC AIMS

The following aims will remedy prior purchase task limitations and will ultimately address important gaps in the drug demand literature:

Aim 1: Validate the Marijuana Purchase Task (MPT) measure via administration to a representative sample of marijuana users and assessment of smoking behavior in the laboratory (*n*=85). Hypothetical MPT responses (e.g., how many hits of marijuana would you take if they cost \$0.25?, \$0.50?, etc...) will be compared to responses on an Actual MPT whereby one of the subject's response choices is selected at random to determine the amount of marijuana to be administered. Marijuana smoking topography will be assessed during a subsequent *ad libitum* smoking session.

- **Aim 1.1**: Test the hypothesis that performance on the Hypothetical MPT will be significantly associated with performance on the Actual MPT.
- **Aim 1.2**: Test hypothesis that marijuana craving post-administration will be lower than craving assessed pre-administration.
- **Aim 1.3**: Test the hypothesis that marijuana puff topography from the *ad libitum* marijuana self-administration session will be related to self-reported grams of cannabis used per week.

B.2. SAMPLE DESCRIPTION AND RECRUITMENT

Participants will be recruited from the community via flyers, advertisements, and social media. Potential subjects will be screened via phone and staff will summarize study procedures. Eligible subjects will be scheduled for an initial laboratory visit. Preliminary data suggests that there is much variability in marijuana use practices; therefore, we will include individuals with a range of use practices and patterns to capitalize on variability. During the initial laboratory visit, participants will provide informed consent and will be enrolled in the study using the following inclusion criteria:

Aim 1: a) marijuana use at least 4 times in the past month on average and at least monthly for the past 6 months; b) English-speaking; c) negative urine toxicology screen for drugs other than marijuana; d) no self-report of other illicit drug use in the past 30 days; e) non-treatment seeking; f) purchase of marijuana at least twice in the past 6 months to confirm familiarity with the construct to be measured; g) negative pregnancy test; h) not nursing; i) use of contraception during the study; j) good physical health; k) zero breath alcohol concentration; l) absence of diagnosis of current depression, mania, psychosis, and panic disorder; m) no self-report of past serious adverse reaction to marijuana; n) no current psychotropic drug use; o) smoking 0-20 tobacco cigarettes per day; p) ability to abstain from marijuana for 15 hours; and q) body mass index in 18.5-30 kg/m² range. In addition, participants must be 18 to 50 years of age. This age range was chosen based on previous marijuana self-administration work [5], [6] to minimize potential cardiovascular risk from smoking marijuana, which increases with age. Participants who test positive for drugs other than marijuana will be given one re-try appointment.

B.3. METHODOLOGY

Aim 1 Approach. Laboratory Sessions: one experimental session (Session 1: controlled paced puff smoking procedure). Participants (n=85) will complete a baseline session with medical screening and two experimental sessions (Session 1: controlled paced puffing smoking procedure; Session 2: ad libitum smoking topography). Following phone screening, subjects will visit the laboratory to provide informed consent. They will be asked to refrain from all marijuana and tobacco smoking for 15 hours, alcohol for 24 hours, and caffeine for 4 hours prior to experimental sessions. Subjects will complete an alcohol breathanalysis, a urine drug screen and pregnancy test (females), and a carbon-monoxide (CO) reading to confirm absence of recent smoking. Subjects with a positive BrAC will be rescheduled. A positive THC screen will be required at this time to confirm marijuana status; however, positive results for other drugs will result in ineligibility. Participants who test positive for drugs other than marijuana will be given one re-try appointment. Participants that do not test positive for marijuana will not be given a re-try appointment. Those with a CO of > 8 ppm will be rescheduled due to the difficulty in confirming overnight marijuana abstinence with higher CO levels [7]–[9]. For those with a CO reading of more than 8ppm during the baseline session, research staff will consult with the PI on a caseby-case basis. PI discretion will be used to ensure the target CO reading of 8ppm is obtained. With respect to the experimental sessions, for those with a CO reading of more than 8ppm at session arrival, PI discretion will be used to ensure the target CO reading of 8ppm will be reached by the onset of marijuana administration. Participants will be allowed one re-test in the event of a CO level above the 8 ppm cut-off when the PI has determined the participant cannot feasibly reach a CO reading of 8ppm in a timely manner on the same date. Tobacco smokers will be allowed to smoke a cigarette following the CO test to prevent nicotine withdrawal. Similar CO-based procedures have been used in marijuana administration studies to avoid the onset of cannabis withdrawal [9]. Subjects will be administered a medical screening questionnaire to rule out history of adverse reaction to marijuana, and a structured clinical interview to rule out Axis I DSM-5 diagnoses. Ineligible subjects will be paid \$10 and excluded from further participation. Eligible subjects will complete baseline measures and undergo a medical screening exam to determine medical clearance prior to the marijuana administration sessions.

Drug: Marijuana (**5.9%** Δ^9 -tetrahydrocannabinol/THC) cigarettes will be provided by the NIDA Drug Supply Program. This dose was selected because administration of **5.9%** THC will closely model potency of marijuana obtained outside the laboratory as marijuana preparations have increased from 3.4% in 1993 to 8.8% in 2008 [10].

Laboratory Session 1: Controlled Paced Puff Smoking Procedure: Subjects will complete the Hypothetical (not associated with marijuana available to smoke) Marijuana Purchase Task (MPT), Actual MPT (identical to Hypothetical MPT but a response choice will be selected at random to determine amount of marijuana available to be smoked), and self-report measures of craving and subjective effects. A blood pressure cuff will be attached to continuously record heart rate (HR) and blood pressure (BP) during the entire experimental session for safety monitoring. Selection of marijuana amount available to smoke: A response choice corresponding to an item price will be randomly selected from the Actual MPT measure completed during the session. Subjects

will draw a number and will be given a monetary budget based on the maximum price set on the MPT measure (\$20) for the marijuana smoking session. Once the response choice/price has been selected, the corresponding number of marijuana hits will be available to smoke, and the subject will receive any remaining money from the monetary budget (e.g., budget=\$20, item selected from Actual MPT =\$5/unit, subject reported he/she would purchase 3 units at this price, 3 units will be available during the smoking procedure, and subject will receive the remaining \$5 from the monetary budget). The controlled paced-puffing procedure [11] includes instructions to "light the cigarette" (30s), "get ready" (5s), "inhale" (5s), "hold smoke in lungs" (10s), and "exhale." The puffing sequence will continue until the subject chooses to cease smoking or the number of available units has been reached (i.e., 20 hits). Subjects are not required to smoke any marijuana as our intention is to assess the relationship between Actual MPT performance and real smoking in the laboratory. Subjects will be informed that the administration session will last 1-hour regardless of number of marijuana hits available. This methodology is based on established procedures that have been successfully used to assess demand for Hypothetical versus Actual alcohol [12]. No more than 20 hits total will be available during the session due to potential safety concerns (e.g., increases in HR which reliably occur [5], [13]).

Laboratory Session 2. *Ad Libitum* Smoking Topography Procedure: Participants will complete baseline measures including the Hypothetical MPT, and will then complete a 1-hour *ad libitum* marijuana self-administration session for assessment of smoking topography. Marijuana cigarettes (5.9% THC) will be smoked through a handheld smoking topography device (CReSSMicroTM). The device will include a holder for the cigarette and study staff will place the cigarette in the device. The subject will light the cigarette and each puff will register immediately upon inhalation. Data from the device will be downloaded and indices of topography will be recorded including number of cigarettes, number of puffs, puff volume (ml), puff duration (ms), average puff velocity (ml/s), and time to peak velocity (ms). Logs will also be maintained by the PI and RA documenting number of puffs smoked and each cigarette or partial cigarette smoked ensuring an accurate count of marijuana cigarettes smoked during the session. These procedures have been successfully used to assess marijuana smoking topography [14]. A maximum of two joints will be available during the session.

Sobriety Assessment: Subjects will receive snacks upon the completion of the administration session. Subjects will remain in the laboratory for 3-hours following the smoking procedure (psychotropic effects of smoked marijuana taper off within 2-3 hours [15]), and will subsequently be evaluated for motor signs of intoxication. Following completion of a field sobriety test [16], subjects will be transported home in a taxi.

Compensation: Participants will be paid \$20 for the baseline session, \$10 for the physical exam, and \$50 for each experimental session (and amount remaining from \$20 tab) for a total of at least \$130 and up to \$150.

Security and Regulatory Aspects for Marijuana: Marijuana cigarettes will be provided by NIDA and will be stored frozen in an airtight container in a locked refrigerator safe located in a cement block room without windows and one door that is locked with code-protected card-key access at [name] on the 3rd floor. Only DEA designated individuals will have access to this room (located in the same building and floor as the location of marijuana administration). Thus, the cigarettes will remain secure at all times. [name] will retrieve a designated number of marijuana cigarettes prior to a scheduled experimental session, humidify them at room temperature for 24 hours before use (per NIDA's instructions) in the same cement block room, and transfer them directly to the laboratory following the start of the session.

Statistical Analysis Plan: The primary aim of this investigation is to confirm the validity of the Marijuana Purchase Task (MPT; primary outcome measure). A linear regression will be performed with marijuana hits purchased on the Actual MPT predicting marijuana hits actually purchased and smoked in the laboratory; baseline total individual income will be included as a covariate. The first secondary aim includes change in marijuana craving pre- and post-marijuana smoking during the experimental session (secondary outcome measure). A two-sided t-test will be conducted to compare craving pre- and post-marijuana smoking. The second secondary aim includes correlation between puffs on the topography device during *ad libitum* marijuana administration and self-reported grams of marijuana used per week (secondary outcome measure).

References

- [1] Office of National Drug Control Policy, "Marijuana Resource Center: State Laws Related to Marijuana | The White House." Accessed: Oct. 29, 2013. [Online]. Available: http://www.whitehouse.gov/ondcp/state-laws-related-to-marijuana
- [2] J. G. Murphy and J. MacKillop, "Relative reinforcing efficacy of alcohol among college student drinkers," *Exp. Clin. Psychopharmacol.*, vol. 14, no. 2, pp. 219–227, May 2006, doi: 10.1037/1064-1297.14.2.219.
- [3] J. J. Palamar, D. C. Ompad, and E. Petkova, "Correlates of intentions to use cannabis among US high school seniors in the case of cannabis legalization," *Int. J. Drug Policy*, Feb. 2014, doi: 10.1016/j.drugpo.2014.01.017.

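### No analysis in the SAP tests Aim 1.1: the primary validity regression does not use the Hypothetical MPT

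*Combined protocol and SAP*

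**What the plan says.** Section B.1 sets out Aim 1 and three numbered hypotheses. Under Aim 1, Hypothetical MPT responses "will be compared to responses on an Actual MPT", and Aim 1.1 is to "Test the hypothesis that performance on the Hypothetical MPT will be significantly associated with performance on the Actual MPT". Aim 1.2 concerns craving before and after smoking. Aim 1.3 concerns puff topography and grams used per week.

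Section B.3, Laboratory Session 1, has participants complete both tasks. The Actual MPT is described as "identical to Hypothetical MPT but a response choice will be selected at random to determine amount of marijuana available to be smoked". Once a price is drawn, "the corresponding number of marijuana hits will be available to smoke". The section adds that "Subjects are not required to smoke any marijuana", because "our intention is to assess the relationship between Actual MPT performance and real smoking in the laboratory". Laboratory Session 2 gives the Hypothetical MPT again, as a baseline measure, without an Actual MPT.

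The SAP paragraph at the end of B.3 names MPT validity as the primary aim and lists three analyses:

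- a linear regression with Actual MPT hits as predictor, hits purchased and smoked as outcome, and baseline income as covariate;
- a two-sided t-test of craving before and after smoking;
- a correlation of topography puffs with self-reported grams per week.

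**The concern.** The study exists to validate a purchase task for later use, and Aim 1.1 is its stated test of whether hypothetical answers track answers that carry real consequences. The SAP's primary analysis uses a different pair of variables. A team that followed the SAP to the letter would reach a conclusion on MPT validity with Aim 1.1 untested. A team that noticed the gap later would have to choose the MPT index and the form of test after the data were in hand.

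A second question concerns the regression itself. The SAP does not say which Actual MPT quantity is the predictor: the response at the drawn price, a total over prices, or another index. On the first reading the predictor limits the outcome, which affects what a significant slope can show.

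**Working it through.** **1. Aims against analyses.**

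| Hypothesis (B.1) | Variables | Matching SAP analysis |
|---|---|---|
| Aim 1.1 | Hypothetical MPT, Actual MPT | none |
| Aim 1.2 | craving before, craving after | t-test |
| Aim 1.3 | puff topography, grams per week | correlation |
| (no numbered aim; intention stated under Session 1) | Actual MPT, hits smoked | primary regression |

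So 1 of 3 hypotheses has no analysis, and 0 of 3 analyses use the Hypothetical MPT.

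**2. Can the regression stand in for Aim 1.1?** The model is smoked = b0 + b1 × Actual + b2 × income + error. It has no Hypothetical term, so b1 and its p-value do not change if every Hypothetical answer is altered. A simulation illustrates this (2,000 runs, n = 85; assumed hits about Normal(8, SD 4) held to 0–20, 85% of purchased hits smoked, two-sided 5%). With true Hypothetical–Actual correlations of 0, 0.3 and 0.9, the regression was significant in 100% of runs each time. A direct Hypothetical–Actual correlation was significant in 4.6%, 78% and 100%. The 100% level reflects the assumed smoking share; what matters is that it does not move.

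**3. What the missing analysis could deliver.** The documents give n = 85 but no alpha, power, effect size or loss rate, so n cannot be re-derived. The figures below assume two-sided 5% and, for the Pearson results, approximate normality.

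- Detectable r at 80% power: tanh[(1.960 + 0.842)/√82] = 0.30. At 90% power: tanh[(1.960 + 1.282)/√82] = 0.34.
- Smallest significant r: t/√(t² + n − 2) = 1.989/√(1.989² + 83) = 0.213, which is 0.213² = 4.5% shared variance.
- 95% CI at an observed r of 0.80: tanh[atanh(0.80) ± 1.960/√82] = 0.71 to 0.87. For a rank correlation, with SE √((1 + 0.80²/2)/82), it is 0.69 to 0.87.
- Half-width of the 95% CI for the paired mean difference: 1.989/√85 = 0.22 SD of the differences.

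With 68 analysable (20% loss, assumed), the last three become 0.239; 0.69 to 0.87 (rank 0.67 to 0.88); and 0.24 SD. Significance alone is therefore a low bar, but the estimates would be usefully precise.

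**4. Why association alone is not enough.** If every Hypothetical answer were twice the Actual one, r would be 1.00 while the mean difference equalled 100% of the Actual mean. Aim 1 promises a comparison of responses, and a correlation would miss this.

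**5. The cap, if the predictor is the drawn-price response.** Then smoked ≤ response. Under Session 1, puffing continues until the subject stops or runs out of available hits, so smoked = min(response, personal stopping point). Three response distributions were assumed (uniform 0–20, uniform 0–5, geometric with mean about 5 capped at 20). Five stopping-point distributions unrelated to the response were also assumed (uniform 0–3, 0–5, 1–5 and 0–10, and geometric with mean 3). The correlation ran from 0.17 to 0.77, and 34% to 100% of samples of 85 passed 0.213. If subjects instead smoke a random share of what is available, unrelated to the response, the correlation reaches about 0.89. Income was left out of these runs.

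**The case against.** The strongest reply is that this is one combined document. B.1 already names both variables, the claim of association and the intention to compare, so Aim 1.1 has not been dropped; only its method is missing. That stands as far as it goes. A reader might infer that the aim was abandoned, and the documents do not support that: both tasks are still collected, side by side, in Session 1. But the gap is more than missing detail, because the analysis labelled primary uses a different pair of variables.

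A second reply is that the SAP's primary, first secondary and second secondary aims run parallel to Aims 1.1, 1.2 and 1.3, so the regression may be a misworded Aim 1.1 analysis. This cannot be settled from the text. The Session 1 statement that "our intention is to assess the relationship between Actual MPT performance and real smoking in the laboratory" suggests that the wording is deliberate. Even if Actual were a slip for Hypothetical, the outcome would be hits smoked, not Actual MPT performance.

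A third reply is that the choice of administration is not really open. That is fair: the Actual MPT is given only in Session 1, so the natural pairing is Session 1 with Session 1. What is open is the index and the form of test.

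Finally, a reader might infer from the cap that a significant slope is all but guaranteed. The documents do not support that. The predictor is not named, and under the protocol's own stopping rule the illustrative correlation can be as low as 0.17, with about a third of samples significant.

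**Conclusion.** The gap is established by the text and needs no numerical assumption: Aim 1.1 has no analysis in the SAP, and the primary regression cannot supply one. It should be closed before analysis, because it concerns the first-listed hypothesis of a validation study.

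The regression is a legitimate question in its own right and a stated intention of the protocol. The reservation about it is conditional. If its predictor is the drawn-price response, some positive slope is expected by design. The size depends on how subjects stop (correlations from about 0.17 to about 0.9 across the assumed models), so significance alone would be weak evidence of validity. The precision and power figures rest on an assumed 5% two-sided level and, for the smaller sample, an assumed 20% loss. They show that the missing analysis is workable at the planned size; they do not measure harm from its absence.

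**What to change.** 1. Confirm whether the primary regression was intended as the Aim 1.1 analysis.
2. Add to the SAP, or correct in it, a pre-specified within-participant analysis of the Session 1 Hypothetical against the Session 1 Actual MPT on one named index, for example total hits over all prices. Report the correlation (rank-based if hit counts are skewed) or slope with a 95% CI, and the mean Hypothetical-minus-Actual difference with a 95% CI.
3. State whether this or the Actual-to-smoked regression is primary, with one sentence on ranking or multiplicity if both are to be.
4. If the regression is kept, name its Actual MPT predictor. If that is the drawn-price response, note that it caps the outcome and interpret the slope accordingly.

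If analysis has already been done, report Aim 1.1 and disclose when its method was chosen.

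The cost is a few SAP sentences and a small amount of extra analysis on data the protocol already collects. Sessions and sample size do not change.

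### Aim 1.1 asks only whether Hypothetical and Actual MPT answers are significantly associated; no agreement estimate is specified, so a systematic over- or under-statement could go unmeasured

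*Combined protocol and SAP*

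**What the plan says.** Section A (Rationale and Overview) gives the goal as to "develop and validate a refined measure for assessment of demand for marijuana to be used in future investigations". Section B.1, under Aim 1, says that Hypothetical responses "will be compared to responses on an Actual MPT". The one hypothesis attached to that comparison is Aim 1.1: "Test the hypothesis that performance on the Hypothetical MPT will be significantly associated with performance on the Actual MPT".

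Section B.3, under Laboratory Session 1, describes the two forms as the same, except that one Actual answer is drawn at random and honoured, while Hypothetical answers have no bearing on what may be smoked. Both forms are completed in Session 1. The Hypothetical form appears again among the Session 2 baseline measures.

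The Statistical Analysis Plan paragraph at the end of B.3 begins: "The primary aim of this investigation is to confirm the validity of the Marijuana Purchase Task". It then gives three analyses:

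- a regression of hits purchased and smoked on Actual MPT hits, with income as a covariate;
- a pre/post comparison of craving;
- a correlation of topography puffs with weekly grams.

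The Hypothetical form is in none of them. Nowhere is there a mean difference, slope or intercept test, concordance or intraclass coefficient, limits of agreement, equivalence margin or minimum correlation for the two forms.

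**The concern.** A significance test of association is a test against zero. It does not ask whether people state the same quantities when nothing is at stake as when something is. A correlation is unchanged if every Hypothetical answer is shifted by a constant or multiplied by a positive constant.

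The design makes such a shift plausible. Actual choices draw on a $20 budget whose remainder the participant keeps; Hypothetical choices cost nothing. Section B.2 also recruits deliberately for varied use. For a given within-person discrepancy, a wider spread between people raises the correlation without improving agreement.

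What is at stake is how the Hypothetical form is described to later users. Stated consumption and expenditure could be well off their real levels while Aim 1.1 is met, and the planned output would not show it, although the paired data are collected.

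**Working it through.** **Inputs from the document.** The sample size comes from B.3: "Participants (n=85) will complete a baseline session with medical screening and two experimental sessions". The criterion is that of Aim 1.1. No alpha or sidedness is given for it; the only sidedness stated concerns craving: "A two-sided t-test will be conducted to compare craving pre- and post-marijuana smoking".

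**Assumptions.** Two-sided alpha 0.05, all 85 participants giving both forms, and a correlation on one hits index per person. The means and SDs below are illustrative.

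**1. The plan's own figure.** n=85 is stated without alpha, power or effect size, so it cannot be reproduced. As a plausibility check on the assumed alpha, Fisher's z with r=0.30 and 80% power gives n = ((1.960 + 0.842)/0.3095)² + 3 = 84.9, or 85. That matches, but r=0.30 and 80% are not in the document.

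**2. Smallest correlation that meets Aim 1.1.** r = t/√(df + t²), with df = 83 and t = 1.989, gives 1.989/√(83 + 3.956) = 0.213. Shared variance is 0.213² = 4.5%. The approximate 95% CI for such an observed r is 0.00 to 0.41.

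| Variant | Critical r |
|---|---|
| n=85, one-sided 0.05 | 0.180 |
| n=85, two-sided 0.05 | 0.213 |
| n=85, two-sided 0.05, income covariate | 0.215 |
| n=85, two-sided 0.05 split over three sub-aims | 0.259 |
| n=85, two-sided 0.01 | 0.278 |
| n=70, two-sided 0.05 | 0.235 |
| n=60, two-sided 0.05 | 0.254 |

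Power at n=85 (two-sided 0.05) is 80% at a true r of 0.30 and 97% at 0.40.

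**3. What a correlation misses.** Lin's concordance coefficient is CCC = 2·r·sA·sH / (sA² + sH² + (mA − mH)²). Take r = 0.9, Actual mean 5 and SD 4.

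- Same mean and SD for Hypothetical: 28.8/32 = 0.90.
- Hypothetical 1.5 times Actual (mean 7.5, SD 6): 43.2/(16 + 36 + 6.25) = 43.2/58.25 = 0.74.
- Hypothetical double Actual (mean 10, SD 8): 57.6/(16 + 64 + 25) = 57.6/105 = 0.55.

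r is 0.9 throughout.

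The session limit of 20 hits does not remove the problem. In simulations with exact doubling and Hypothetical answers capped at 20, an Actual mean of 6 and SD of 3 gave r about 0.99, CCC about 0.44 and a mean excess of about 5.8 hits. A mean of 8 and SD of 5 gave r about 0.92, CCC about 0.57 and again about 5.8 hits.

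**4. Is n=85 enough to estimate agreement?** The 95% CI half-width for a paired mean difference is t/√n = 1.989/√85 = 0.216 SD of the differences. In the doubling example that SD is √(16 + 64 − 57.6) = 4.73, so the difference of 5 hits would have a CI of about ±1.0 hit. In the 1.5-fold example the SD is √(16 + 36 − 43.2) = 2.97, so the difference of 2.5 hits would have a CI of about ±0.6. An observed intraclass correlation of 0.80 would have an approximate 95% CI of 0.71 to 0.87. The sample is adequate for this purpose.

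**The case against.** The strongest reply is that no rule in the document equates a significant Aim 1.1 with validation. The SAP ties the primary validity claim to a different analysis, Actual MPT hits predicting hits purchased and smoked. A reader might infer that the measure as a whole would be declared valid at r of about 0.21. The document does not say that, and this point does not claim it.

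Other parts of the reply also have weight:

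- Aim 1.1 speaks of association, not of a Pearson correlation. If the SAP's regression approach were carried over, regressing Hypothetical on Actual would give a slope of 0.9 × 8/4 = 1.8 in the doubling example, so scaling need not stay hidden. But no such regression is specified, and its significance test would still be against a slope of zero.
- The promise in Aim 1 to compare the forms could include a difference analysis. It names no method, and the SAP supplies none.
- If later users only need to rank people, association is relevant evidence. That is a reason to keep it, and not to call it the wrong question outright.
- Both forms are completed in Session 1, so remembered answers may inflate agreement as well as correlation. Agreement on these data would not by itself settle hypothetical bias.

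A reader might also infer that price elasticity would be biased. Uniform doubling at every price leaves point elasticity unchanged. A bias in elasticity needs an error that varies with price, and nothing in the document shows one.

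**Conclusion.** The point stands in a limited form. As written, the plan asks only for a significant association between the two forms and specifies no estimate of agreement, although its goal is validation and the forms differ only in the reward. The threshold of about 0.21 rests on assumed two-sided alpha 0.05 and 85 completers, with a range of about 0.18 to 0.28 at n=85 under other alphas and sidedness. The fall in concordance to 0.74 or 0.55 rests on illustrative means and SDs. That a correlation ignores uniform shifts and scaling depends on none of these figures.

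This should be changed, but it does not undermine the study, because the paired data permit the better analysis. It is related to the absence of any Hypothetical-versus-Actual analysis in the SAP, and one edit can close both. Adding only the association as Aim 1.1 words it would leave this gap open.

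**What to change.** Amend Aim 1.1 and the SAP together:

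1. Name the MPT index and which Hypothetical administration (Session 1 or Session 2) is used.
2. Estimate the paired Hypothetical-minus-Actual difference in hits, overall and by price, with 95% CIs. Use a mixed model with version, price, version-by-price and participant random effects, including one for the version contrast so that repeated prices are not counted as independent evidence about it.
3. Report a concordance coefficient with 95% CI on the named index.
4. State alpha and sidedness, and fix in advance the difference or concordance that would be acceptable, with reasons. Without such a limit the new criterion would be as open as the present one.
5. Base the statement about the validity of the Hypothetical form on these estimates, and keep the association as supportive.
6. State as a limitation that completing both forms in Session 1 may inflate agreement. Make no claim about elasticity unless the version-by-price results show price-dependent error.

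The cost is a reworded aim, a short SAP paragraph and slightly more analysis, with no new data. The result may look less favourable than a significant correlation.

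### The Session 1 stopping rule equates available units with 20 hits, while the same procedure sets them at the number bought at the drawn price; the two must be reconciled

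*Combined protocol and SAP*

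**What the plan says.** All the administration text is in section B.3 (Methodology), under Laboratory Session 1.

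- **Purpose of the draw.** The Actual MPT differs from the Hypothetical MPT in that "a response choice will be selected at random to determine amount of marijuana available to be smoked".
- **Definition of what is available.** "Once the response choice/price has been selected, the corresponding number of marijuana hits will be available to smoke".
- **Budget.** The participant "will be given a monetary budget based on the maximum price set on the MPT measure (\$20") and keeps what is not spent.
- **Worked example.** At $5 per unit, "subject reported he/she would purchase 3 units at this price, 3 units will be available during the smoking procedure", and the "subject will receive the remaining \$5 from the monetary budget".
- **Stopping rule.** The paced puffing continues "until the subject chooses to cease smoking or the number of available units has been reached (i.e., 20 hits").
- **Session maximum.** The procedure closes with: "No more than 20 hits total will be available during the session due to potential safety concerns".

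The Statistical Analysis Plan paragraph, also in B.3, regresses "marijuana hits actually purchased and smoked in the laboratory" on hits purchased on the Actual MPT, with baseline income as a covariate.

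**The concern.** The definition and the example make the available number specific to each participant and each drawn price. The parenthesis in the stopping rule makes it 20 for everyone. The abbreviation it uses signals identity, not an example or an upper limit, so on its face the rule redefines the term it was meant to apply.

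Two things depend on that sentence. First, it is the instruction by which staff end administration of 5.9% THC cigarettes. Second, it sets the upper bound on hits smoked. If the sequence ends at the number bought, hits smoked cannot exceed hits bought at the drawn price. If it ends at 20, they can, and the participant would still receive the money left from the smaller purchase. Smoking would then no longer carry the monetary consequence that distinguishes the Actual task from the Hypothetical one. If staff read the sentence differently from one another, the dependent variable would have different upper bounds in different participants.

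**Working it through.** **Inputs, all from Laboratory Session 1 in B.3 unless noted:** budget $20; example price $5; example purchase 3 units; figure in the stopping rule 20 hits; session maximum 20 hits; top MPT price $20. Aim 1 in B.1 also mentions prices of $0.25 and $0.50. The documents do not list the full set of prices, so $1, $2 and $10 below are illustrative.

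**Step 1: reproduce the plan's own figure.** Refund = budget − price × units = 20 − 5 × 3 = $5. This matches the example, so the example is internally sound with 3 units available.

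**Step 2: apply the stopping rule's figure to the same example.** The difference is 20 − 3 = 17 hits. At $5 each, 20 hits would cost 20 × 5 = $100, against a budget of $20.

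**Step 3: find where the two statements can agree.** Assume that a participant cannot buy more than the budget covers. The most that can be bought is then 20 ÷ price, rounded down to whole hits. Twenty hits are affordable only if price ≤ 20 ÷ 20 = $1.

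| Price per hit | Most hits $20 can buy | Most available under the 20-hit maximum | Smallest gap to the rule's 20 |
|---|---|---|---|
| $0.25 | 80 | 20 | 0 |
| $0.50 | 40 | 20 | 0 |
| $1 | 20 | 20 | 0 |
| $2 | 10 | 10 | 10 |
| $5 | 4 | 4 | 16 |
| $10 | 2 | 2 | 18 |
| $20 | 1 | 1 | 19 |

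The last column is a minimum, because it supposes that the participant spends as much of the budget as possible. In the example the participant buys 3, not 4, so the gap is 17 and not 16. At $1 or less the gap is zero only for a participant whose choice reaches 20.

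**Step 4: check what depends on the budget assumption.** The contradiction does not: the example says 3 and the rule says 20 whatever the budget. Only the $1 threshold and the table use the assumption.

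**The case against.** The strongest reply is that the surrounding text already settles the meaning. The operative condition is that the available units have been used up. The draw, the definition and the example all say how that number is fixed. The procedure also notes that the session lasts one hour however many hits are available, which implies that the number varies. The closing sentence explains where 20 comes from. Read together, these suggest a single intended rule with one careless parenthesis. That reading is probable, and it lowers the severity. It does not remove the conflict, because the parenthesis sits in the sentence that staff follow, and the maximum is already stated separately.

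A reader might infer three stronger things that the documents do not support.

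- **That the protocol plans to give participants hits they did not buy.** Nothing shows this. It would require staff to set aside the definition, the example and the refund on the strength of one parenthesis. The gap of 17 hits measures the disagreement between the statements; it is not an expected overrun. The 20-hit maximum and the participant's freedom to stop hold on either reading.
- **That the primary outcome is invalidated.** The Statistical Analysis Plan names the MPT as the primary outcome measure. Hits smoked is the dependent variable of the regression, and it is worded as hits both purchased and smoked, so unpurchased hits fall outside it as written.
- **That Session 1 puffs go unrecorded.** Puff logs are described only under Laboratory Session 2. That leaves Session 1 records unspecified; it does not show that none are kept.

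**Conclusion.** The point stands as an internal contradiction, probably a slip of wording, in a sentence with practical force. Within Laboratory Session 1, available units are the number chosen at the drawn price and also a fixed 20. The size of the disagreement is 17 hits in the protocol's own example, and at least 10, 16, 18 and 19 hits at $2, $5, $10 and $20. The example figure needs no assumption; the others assume that purchases stay within the $20 budget.

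The consequences for the regression and for exposure are conditional on literal or uneven application of the rule. It is worth correcting because the sentence governs administration and bounds the regression's dependent variable. This review does not say which limit should apply.

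**What to change.** Reconcile the Laboratory Session 1 text so that the stopping rule, the definition of available units, the worked example and the session maximum are consistent, with one stated meaning for the number at which the sequence ends. The choice of that number belongs to the investigator and sponsor.

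Make sure that Session 1 records show, for each participant, the hits purchased at the drawn price and the hits smoked. The regression variable can then be derived as worded, and any difference between the two counts can be seen.

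The cost is one sentence in the protocol and minor record-keeping. No added procedures or participants are needed.
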